4.8.3 Prior and Concomitant Medications

All medications will be collected from the time the subject signs the informed consent form throughout the subject's participation in the study, including a period of 30 days after the subject's last dose of study drug.

For each concomitant medication taken during the trial, the generic component will be identified using the World Health Organization Drug Dictionary (WHO-DD; WHODDB3 ENHANCED JUN 2015).

Medications will be assigned to a time period (prior and/or concomitant) as follows:

- If both the start and stop date exist and are before the first dose date of study drug, the medication will be counted as prior.
- If the start date is on or after the first dose date of study drug, the medication will be counted as concomitant.

- If the start date is before the first dose date of study drug and the stop date is after the first dose date of study drug or the medication is continuing, the medication will be counted as prior and concomitant.
- If the start date is missing and the stop date is before the first dose of study drug, the medication will be counted as prior.
- If the start date is missing and the stop date is after the first dose of study drug or the medication is continuing, the medication will be counted as concomitant.
- If the start and stop dates are missing, the medication will be counted as concomitant.

Summaries showing number of subjects and percentage taking each medication will be provided for each preferred medication term by treatment arm. This will be done separately for prior and for concomitant medications.

A by-subject listing of all prior and concomitant medication data will also be provided.

4.8.4 Clinical Laboratory Evaluation

Local laboratories will be used for laboratory safety evaluations in this study. For a list of the parameters to be evaluated, see Section 3.2.2 of this SAP. Laboratory normal ranges will be provided by the local laboratory. For parameters where an NCI CTCAE v.4.03 scale exists, laboratory results will be graded according to the NCI CTCAE v.4.03 severity grade. For parameters for where an NCI CTCAE v.4.03 scale does not exist, an indicator of whether the value is below, within, or above the normal range will represent severity instead.

All laboratory values will be reported in SI units.

Summaries for each laboratory parameter will be presented by treatment arm and visit. For by-visit summaries, the first non-missing assessment (including repeat assessments) recorded at each visit will be used. Optional laboratory parameters will not be summarized by treatment arm, only listed.

For laboratory values reported as a character value, such as <40, will be transformed into numerical values for summary reasons by following the specified guidelines. If a laboratory value is reported using the less than symbol, '<', 0.10 will be subtracted from the original numeric value. If a laboratory value is reported using the greater than symbol, '>', 0.10 will be added to the original numeric value.

Observed and change from baseline values in laboratory test results will be analyzed using descriptive statistics (except for parameters with categorical results, which will use frequencies and percentages). Change from baseline will only apply to post-baseline assessments for parameters with continuous results. For each lab parameter at each time point, the difference in mean changes from baseline (tivozanib – sorafenib) using a rank-

sum test will be presented along with the 95% CI. Laboratory results will also be summarized by maximum CTC grade or by worst severity, depending on the parameter.

Shifts in grade from baseline to each post-baseline visit will be summarized by treatment arm. The maximum shift (across all visits) from baseline will also be summarized by treatment arm. If needed, significance of shifts in laboratory parameters may be further evaluated within each treatment arm using a generalized McNemar's test.

A by-subject listing of all laboratory data, with abnormal values flagged, will be provided by treatment arm. This listing will include center, patient identifier, age, gender, race, weight, and visit, as well as laboratory reference ranges for each parameter. A similar listing with out-of-reference range values will also be presented.

4.8.5 Vital Signs, Physical Findings and Other Observations Related to Safety

A description of vital sign parameters, ECG results, ECOG performance status, and physical examination can be found in Section 3.2.2 of this SAP.

Summaries for each vital sign parameter will be presented by treatment arm and visit. Observed and change from baseline values in vital sign results will be analyzed using descriptive statistics. Change from baseline will only apply to post-baseline assessments. For each vital sign parameter at each time point, the difference in mean changes from baseline (tivozanib – sorafenib) using a rank-sum test will be presented along with the 95% CI.

Shifts in ECG results, ECOG performance status, and physical examination from baseline to each post-baseline visit (where available) will be summarized by treatment arm. The maximum shift (across all visits) in ECG results and ECOG performance status from baseline will also be summarized by treatment arm.

For systolic blood pressure (SBP) and diastolic blood pressure (DBP), observed values will be classified as markedly abnormal (MA) or not markedly abnormal (NMA). The criteria for determining MA values are as follows:

- SBP <=80 mmHg or >=180 mmHg
- DBP <=50 mmHg or >=105 mmHg

The number and percentage of subjects with MA change values will be summarized for each vital sign parameter by treatment arm and visit.

By-subject listings of vital sign data, ECG results, ECOG performance status, and physical examination results will be provided by treatment arm.

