4.2 General Presentation Considerations

'Baseline' is defined as the last observation on or before Cycle 1 Day 1. Baseline assessments should occur within 7 days of Cycle 1 Day 1. 'End of Treatment' is defined as the last available observation up to 7 days after the last dose of study treatment. 'End of Study' is defined as the last available observation after 'End of Treatment'.

Durations are calculated as the stop date minus the start date plus one.

For elapsed time (e.g. time since the initial diagnosis) if the reference date is on or after the event date, then the elapsed time is the reference date minus the event date plus one. If the reference date is before the event date then the elapsed time is the reference date minus the event date.

Unscheduled assessments (laboratory data, ECG, or vital signs associated with nonprotocol clinical visits or obtained in the course of investigating or managing adverse events) will be included in listings, but not summaries. If more than one laboratory value is available for a given visit, the first valid observation will be used in summaries and all observations will be presented in listings. If it is not possible to determine which is the first measurement due to missing times then the average of all measurements for that time point will be used as the value for that time point.

Continuous data will be summarized in terms of the mean, standard deviation (SD), median, minimum, maximum, and number of observations, unless otherwise stated. Continuous data that are expected to be skewed will be presented in terms of the maximum, upper quartile, median, lower quartile, minimum, and number of observations. The minimum and maximum will be reported to the same number of decimal places as the raw data recorded in the database. The mean, median, lower quartile, and upper quartile will be reported to one more decimal place than the raw data recorded in the database. The SD will be reported to two more decimal places than the raw data recorded in the database. In general, the maximum number of decimal places reported shall be four for any summary statistic.

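### SAP 4.8.5 gives no any-time count by arm of markedly high blood pressure, puts low and high readings under one flag, and misnames what it tabulates (minor)

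*SAP*

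**What the plan says.** SAP 4.8.5 defines the flag on values as measured: "observed values will be classified as markedly abnormal (MA) or not markedly abnormal (NMA"). Each limit is two-sided: "SBP <=80 mmHg or >=180 mmHg" and "DBP <=50 mmHg or >=105 mmHg". No other vital sign has a limit. The table is then described as follows: "The number and percentage of subjects with MA change values will be summarized for each vital sign parameter by treatment arm and visit".

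Other safety data get a worst-value summary over the whole study. For laboratory results, SAP 4.8.4 says "Laboratory results will also be summarized by maximum CTC grade or by worst severity, depending on the parameter", and also "The maximum shift (across all visits) from baseline will also be summarized by treatment arm". SAP 4.8.5 adds, for two further measures, "The maximum shift (across all visits) in ECG results and ECOG performance status from baseline will also be summarized by treatment arm". Blood pressure has no equivalent.

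Unscheduled readings are excluded from the table. SAP 4.2 says that unscheduled vital signs, among other assessments, including those "obtained in the course of investigating or managing adverse events) will be included in listings, but not summaries". SAP 3.1 says the same. Protocol 14.3.5 asks only for a descriptive summary of vital signs by visit and arm, and the SAP meets that.

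**The concern.** The expected harm runs in one direction. Protocol 3.6.2 reports hypertension in TIVO-1 in 44.0% on tivozanib against 34.2% on sorafenib, and Grade 3 or higher in 24.7% against 17.1%. TIVO-1 was a different population (about 70% had no prior systemic therapy for metastatic disease), so those rates need not carry over, but the signal does.

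Whether a reading becomes an adverse event depends partly on the investigator's view of clinical significance (Protocol 12.1.1), and the investigator knows the treatment. A per-subject count of measured high pressure does not pass through that judgement. The planned table does not give it, for three reasons:

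- it is broken down by visit;
- it leaves out unscheduled readings;
- it merges low with high.

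The timing of scheduled visits adds to the case. After Cycle 1, the per-cycle reading is on Day 1 before dosing, when a tivozanib subject has normally just finished the off-drug week and a sorafenib subject has been dosing continuously. What is at stake is the clarity of one safety table. No efficacy inference is involved.

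**Working it through.** The plan states no figure on this point, so there is nothing to reproduce. The check compares the text of the sections and then bounds what a by-visit table leaves open.

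**1. Wording.** The limits apply to observed values of two parameters. The table sentence refers to changes and to every vital sign. SAP 3.2.2 also lists heart rate, respiration rate and temperature, for which no limit exists. The table cannot be programmed as written without a guess. The likely intent is observed MA values of SBP and DBP; a move from not-MA at baseline to MA afterwards is a second possible reading.

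**2. Pooling.** SBP cannot be both ≤80 and ≥180 in one reading, so at a given visit: pooled count = low count + high count ≥ high count. Pooling cannot understate high readings, but it can hide direction. Assumed example: 10% high + 2% low = 12% in one arm, and 5% high + 7% low = 12% in the other. The pooled rows match while the high readings differ two-fold.

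**3. Number of scheduled readings.** Visits come from Protocol Table 1. Treatment is assumed to last the planning medians for PFS (SAP 4.9), with one month = 365.25/12 = 30.44 days.

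- 4 months = 121.75 days: Cycle 1 Day 15, plus Day 1 of Cycles 2 to 5 (Days 29, 57, 85, 113), plus End of Treatment = 6.
- 6 months = 182.6 days: Cycle 1 Day 15, plus Day 1 of Cycles 2 to 7 (Days 29 to 169), plus End of Treatment = 8.

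The 30-day visit has a ±7-day window. It falls inside the SAP's treatment-emergent window (before 30 days after last dose) only if held early, in which case the counts become 7 and 9.

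**4. Any-time share.** Let p be the proportion markedly high at each of k visits, with everyone attending. Then

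p ≤ any-time share ≤ min(1, k × p).

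The lower end means the same subjects every time; the upper end means different subjects each time. With 161 per arm, all assumed treated:

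| p (assumed) | k | lower | upper |
|---|---|---|---|
| 1% | 6 | 1% (about 2) | 6% (about 10) |
| 1% | 8 | 1% (about 2) | 8% (about 13) |
| 2% | 6 | 2% (about 3) | 12% (about 19) |
| 2% | 8 | 2% (about 3) | 16% (about 26) |
| 5% | 6 | 5% (about 8) | 30% (about 48) |
| 5% | 8 | 5% (about 8) | 40% (about 64) |

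Independence between visits, 1 − (1 − p)^k, gives 11.4% (k = 6) and 14.9% (k = 8) at p = 2%. It is a point inside the range and not its upper limit. The by-visit rows look the same anywhere in the range, so they cannot be converted into a per-subject count.

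**5. Timing against dosing.** Assessments precede that day's dose (Protocol 7.1). Tivozanib is given for 21 days and then stopped for 7 (7.2.1); sorafenib is continuous (7.2.2). Day 1 readings from Cycle 2 on therefore normally follow about a week without tivozanib. Cycle 1 Day 15 is the only scheduled post-baseline visit placed within a dosing period; End of Treatment may come up to 7 days after the last dose. With the mean half-life of about 4.7 days (Protocol 3.6.1), roughly 2^(−7/4.7) = 0.36 of the concentration remains after 7 days, so exposure is reduced but not absent. Protocol 3.7.2 describes toxicities as quickly reversible once dosing stops. Neither fact gives a blood-pressure difference.

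**The case against.** The strongest reply is that this asks for one more table where the signal is already well covered:

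- SAP 4.8.2 counts hypertension per subject by maximum CTCAE grade.
- SAP 4.8.5 gives the between-arm difference in mean change at each time point with a 95% CI, without any adverse-event judgement.
- SAP 4.2 puts minimum and maximum in the continuous summaries, so each visit shows whether any scheduled reading reached a limit.
- SAP 4.8.3 tabulates concomitant medications, which picks up antihypertensives, and 4.8.1 gives reasons for dose reduction and interruption.
- All readings are listed, so the count could be derived later.

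Investigator discretion is also limited. Protocol 12.1.1 requires reporting when a finding needs medical intervention, and 10.4.1 requires antihypertensive treatment before a tivozanib dose reduction for hypertension. The protocol's own requirement is met, the exclusion of unscheduled data is a general convention, and physical examination has no across-visit maximum either.

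Most of this stands, and it is why the point is minor. It does not supply the missing number. Mean changes say little about the tail, by-visit extremes show that someone crossed a limit but not how many, and medication use is indirect. A count taken from listings afterwards would not be pre-specified.

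A reader might go further and infer that the plan understates hypertension, or that the off-drug week makes tivozanib look better. The documents do not support either. Pooling cannot lower a count, the adverse-event route remains open, and neither the size nor the direction of any timing effect on blood pressure can be derived.

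**Conclusion.** The point holds as a minor, inexpensive improvement to safety reporting. The change wording needs correcting in any case. The substantive gap is that no planned table gives, by arm, the number of subjects with a markedly high measured pressure at any time, for a known harm in an open-label trial whose per-cycle readings after Cycle 1 normally follow tivozanib's off week.

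No figure for this trial can be derived. The bounds rest on an assumed, constant per-visit rate, full attendance and treatment lasting 4 to 6 months. Their lower end means that nothing is lost. They apply to both arms alike, so no between-arm distortion is shown. The effect of omitting unscheduled readings cannot be quantified from the documents.

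**What to change.** In SAP 4.8.5:

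1. Tabulate MA observed values, for SBP and DBP only, with separate rows for markedly high (SBP ≥180; DBP ≥105) and markedly low (SBP ≤80; DBP ≤50).
2. Add, by arm in the safety population, the number and percentage of subjects with any treatment-emergent markedly high SBP or DBP, meaning after first dose and before 30 days after last dose, in line with the window in SAP 3.2.2. Show subjects already markedly high at baseline separately. The eligibility rule (Protocol 6.2, criterion 6) concerns pressure uncontrolled on two or more drugs, so such subjects are possible.
3. Give one row for scheduled visits only and one that includes unscheduled readings. Footnote that unscheduled measurement is made when clinically indicated and may differ between open-label arms.

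The cost is a wording change and one small table from data already collected. The drawback is possible unequal ascertainment in the unscheduled row, which is why the scheduled-only row should stand beside it.

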4.8.6 Safety Monitoring Committee

The objectives of the Safety Monitoring Committee (SMC) are to evaluate interim safety data to protect subject welfare and to identify issues and risks, as well as to provide

recommendations regarding study design and conduct. The SMC is composed of six members, all of whom are qualified clinicians in general oncology and renal cell carcinoma and have practical experience conducting and monitoring the safety and efficacy of clinical trials.

A meeting to review cumulative safety data will be planned after the first 50 subjects are randomized to each treatment arm and approximately every 6 months thereafter. There may be additional ad hoc meetings (via teleconference or face-to-face) to evaluate the safety of the subjects, when internal reviews detect safety risks. The frequency may be modified at the discretion of the SMC

After each meeting, the SMC will make recommendations to modify or terminate the trial if there is a safety concern or a significant emerging issue with trial design or conduct. Further details on the Safety Monitoring Committee activities can be found in the SMC Charter.

4.9 Determination of Sample Size

A sample size of 322 subjects (161 subjects per treatment arm) with a total number of 255 events will provide 90% power to detect a statistically significant difference between treatment arms with respect to PFS as assessed by the IRR. The sample size was determined based on the following assumptions:

- The distribution of the PFS for the two treatment arms will be compared by using a log-rank test with one-sided 2.5% significance level.
- The median PFS for subjects receiving sorafenib and tivozanib is 4 months and 6 months, respectively (an increase of 2 months or 50%).
- An equal number of subjects will be assigned to each treatment arm.
- Enrollment will take 15 months.
- The drop out percentage per treatment arm will be 3%.

The first secondary analysis will compare OS between sorafenib and tivozanib by using a stratified log-rank test (stratification factors included in the primary analysis), and twosided 0.8% significance level (utilizing a Lan-DeMets alpha spending function with an O'Brien Fleming boundary). The interim OS analysis will be done at the time of the final PFS analysis. Assuming a median OS for sorafenib of 12 months and a median OS for tivozanib of 16 months, 245 OS events at the time of final OS analysis and 149 OS events at the time of final PFS analysis will yield approximately 61% power to demonstrate longer OS for tivozanib using the log-rank test, given 2.5% type I error (one-sided). The final OS analysis will be performed when all subjects have been lost to follow-up, have withdrawn consent, have died, or when all subjects in follow-up have been on-study for at least 2 years, whichever occurs first.

The estimate was obtained by using East® statistical package Version 6.3 by Cytel Inc.

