1 SYNOPSIS

Name of sponsor/company: AVEO Pharmaceuticals, Inc.	
Name of investigational product: Tivozanib Hydrochloride (AV-951) capsules	
Title of study: A Phase 3, Randomized, Controlled, Multi-Center, Open-Label Study to Compare Tivozanib Hydrochloride to Sorafenib in Subjects With Refractory Advanced Renal Cell Carcinoma	
Study Number: AV-951-15-303	
Estimated number of study center(s): Approximately 160-190 centers	
Study duration (years): Estimated date first subject enrolled: June 2016 Estimated date last subject enrolled: August 2017 Established data cut-off date: 04 October 2018	Phase of development: 3
Objectives: Primary: 
To compare the progression-free survival (PFS) of subjects with refractory advanced renal cell carcinoma (RCC) randomized to treatment with tivozanib hydrochloride (tivozanib) or sorafenib as assessed by blinded independent radiological review (IRR) of computerized tomography (CT) or magnetic resonance imaging (MRI). Secondary: 
To compare the overall survival (OS) of subjects randomized to treatment with tivozanib or sorafenibTo compare objective response rate (ORR) and duration of response (DoR) of subjects randomized to treatment with tivozanib or sorafenibTo compare the safety and tolerability of tivozanib and sorafenib. Tertiary: 
To explore any relationship between:
tivozanib and sorafenib drug levels and activitytivozanib and sorafenib drug levels and adverse events (AEs)	
Methodology: Open-label, randomized, controlled, multi-national, multi-center, parallel-arm study. Subjects will be randomized in a 1:1 ratio (tivozanib: sorafenib) stratified by the International Metastatic Renal Cell Carcinoma Database Consortium (IMDC) risk category (favorable; intermediate; poor) and prior therapy (two prior vascular endothelial growth factor [VEGF] receptor tyrosine kinase inhibitors [VEGFR TKIs]; a prior checkpoint	

Name of sponsor/company: AVEO Pharmaceuticals, Inc.
Name of investigational product: Tivozanib Hydrochloride (AV-951) capsules

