Duration of treatment: Subjects with documented stable disease or an objective response may continue to receive therapy at the same dose and schedule until progression as long as tolerability is acceptable. Discontinuation: Subjects experiencing unacceptable toxicities will be discontinued from further study treatment. Subjects with radiological evidence of progressive disease per investigator/local radiology assessment should continue treatment until progressive disease is verified by an independent radiologist. Images should be submitted for independent review as soon as possible (see Imaging Manual for specific instructions). Verification is not required in the following circumstance: 
• Significant clinical deterioration that is indicative of progressive disease Subjects who have documented disease progression will be discontinued from the study treatment. Follow-up: Each subject will be followed until death from any cause (unless the subject is lost to follow-up, withdraws consent for the entire study, or the Sponsor terminates the study early). Once discontinued from study drug treatment, all subjects are to be followed for evidence of new onset of adverse events, and to ensure resolution or stabilization of existing ongoing adverse events, for 30 days from the last dose of study drug. After the 30-Day Follow-up Visit, subjects will be contacted by the site once every 3 months to collect long-term survival data.
Statistical methods: A sample size of 322 subjects (161 subjects per treatment arm) with total number of 255 events will provide 90% power to detect a statistically significant difference between treatment arms with respect to PFS as assessed by an

Name of sponsor/company: AVEO Pharmaceuticals, Inc.

Name of investigational product: Tivozanib Hydrochloride (AV-951) capsules

IRR. The sample size was determined based on the following assumptions:

- The distribution of the PFS for the 2 treatment arms will be compared by using a Log-rank test with a two-sided 5% significance level (α)
- The median PFS for subjects receiving sorafenib and tivozanib is 4 months and 6 months, respectively, (an increase of 2 months or 50%)
- Equal numbers of subjects will be assigned to each treatment arm
- Enrollment will take 15 months
- The drop out percentage per treatment arm will be 3%

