Data will be summarized using descriptive statistics (number of subjects, mean, median, standard deviation, minimum, and maximum) for continuous variables and using frequency and percentages for discrete variables.

The primary analysis will compare the distribution of the PFS between the two treatment arms by using the stratified Log-rank test, in which the stratification factors are IMDC risk category (favorable; intermediate; poor) and prior therapy (two prior VEGF TKIs; a prior checkpoint inhibitor [PD-1 or PD1-L inhibitor] plus a prior VEGFR TKI; a prior VEGFR TKI plus any other systemic agent). PFS will be based on the CT or MRI scan assessed by the IRR. PFS graphs will be presented by treatment arm.

The first secondary analysis will compare OS between the 2 treatment arms by using the stratified Log-rank test, the stratification factors included in the primary analysis, and two-sided 0.8% significance level (utilizing a Lan-DeMets alpha spending function with an O'Brien-Fleming boundary). An interim OS analysis will be done at the time of the final PFS analysis. It is expected that 149 OS events would have occurred at the time of final PFS analysis.

An interim analysis will be performed after 128 PFS events have been observed. The interim analysis will look into the study's futility using PFS as the efficacy evaluation endpoint. This will utilize a Lan-DeMets error spending-type function with an O'Brien-Fleming stopping boundary with an estimated two-sided beta (Type II error) of 1.2 % spent during this interim look. The interim analysis will be performed by an independent statistician. The independent statistician will evaluate and interpret the results of the interim analysis and will provide corresponding recommendation whether to stop the study for futility or for the study to continue until end of study condition has been met.

Two populations will be defined for the efficacy analysis: Intent-to-treat (ITT; defined as all subjects who were randomized into the study) and per protocol (PP; defined as all subjects in the ITT population who did not have major protocol deviations, have received at least two cycles (8 weeks) of protocol treatment, and met all eligibility criteria). Primary efficacy analysis will be based on ITT where subjects will be analyzed as randomized.

The safety population (SAF) will include all subjects who received at least one dose of either study drug. Subjects will be analyzed as treated.

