14.2 Sample Size Justification

A sample size of 322 subjects (161 subjects per treatment arm) with total number of 255 events will provide 90% power to detect statistically significant differences between treatment arms with respect to progression-free survival as assessed by the independent radiology review. Analysis of the primary endpoint will occur after 255 events have occurred. A simulation indicates that the analysis could be performed ≥ 6 months after the last subject is accrued. The sample size was determined based on the following assumptions:

- The distribution of the PFS for the two treatment arms will be compared by using a Log-rank test with two-sided 5% significance level (α).
- The median PFS for subjects receiving sorafenib and tivozanib is 4 months and 6 months, respectively (an increase of 2 months or 50%).
- An equal number of subjects will be assigned to each treatment arm.
- Enrollment will take 15 months.
- The drop out percentage per treatment arm will be 3%.

The first secondary analysis will compare OS between the 2 treatment arms by using stratified Log-rank test, the stratification factors included in the primary analysis, and two-sided 0.8% significance level (utilizing a Lan-DeMets alpha spending function with an O'Brien-Fleming boundary). The interim OS analysis will be done at the time of the final PFS analysis. Assuming a median OS for sorafenib of 12 months and a median OS for tivozanib of 16 months, 245 OS events at the time of final OS analysis and 149 OS events at the time of final PFS analysis will yield approximately 61% power to demonstrate longer OS for tivozanib using the log-rank test, given 2.5% type I error (one-sided). The final OS analysis will be performed when all subjects have been lost to follow-up, have withdrawn consent, or have died, or when all subjects in follow-up have been on-study for at least 2 years, whichever occurs first.

The estimate was obtained by using East[®] statistical package Version 6.3 by Cytel Inc.

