4.7.1.4 Multiple Comparisons/Multiplicity

There will be no adjustment for multiplicity. PFS with one treatment contrast (tivozanib vs. sorafenib) is the only primary analysis defined for this study. The secondary analyses are simply intended to provide supportive evidence relating to the primary analysis, therefore, all efficacy endpoints will be assessed without adjustment for multiple comparisons.

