4.7.3 Secondary Efficacy Variables

Overall Survival

The first secondary analysis will compare OS between the two treatment arms by using a stratified log-rank test and the stratification factors included in the primary analysis. The hazard ratio for treatment will be estimated using the stratified Cox proportional hazards regression model.

Summaries showing the 1- and 2-year survival probabilities and corresponding 95% CIs will be provided along with graphical displays (similar to PFS).

Objective Response Rate

The number and proportion of subjects achieving confirmed OR (i.e. confirmed CR or confirmed PR) will be summarized and presented by treatment arm and cycle for the ITT population using a Cochran-Mantel-Haenszel (CMH) test (α =0.05) with the same stratification factors used for the PFS analysis. The odds ratio and associated 95% CI will be calculated. If the expected number in at least one cell is too small (<5), then Fisher's exact test will be used.

In addition, the BOR for each subject will be summarized (number and percentage of subjects in each category).

Duration of Response

Summaries and graphical displays for DoR will be similar to those of OS. This analysis, however, will only apply to subjects that have achieved confirmed OR.

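### The two-sided 0.8% printed for overall survival is only the interim level; the final level (about 4.74%) is not stated, and the protocol still triggers the PFS analysis at 255 events against a cut-off targeting 242

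*SAP*

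**What the plan says.** **OS level.** The synopsis describes the first secondary analysis as a stratified log-rank comparison with "the stratification factors included in the primary analysis, and two-sided 0.8% significance level", citing Lan-DeMets spending with an O'Brien-Fleming boundary. Protocol 14.2 says the same, and so does SAP 4.9, which gives the level as "0.8% significance level (utilizing a Lan-DeMets alpha spending function". A separate sentence places an interim OS analysis at the final PFS analysis. Protocol 14.2 and SAP 4.9 then assume median OS of 12 and 16 months and 245 deaths at the final analysis, and state that "149 OS events at the time of final PFS analysis will yield approximately 61% power to demonstrate longer OS for tivozanib", at a one-sided 2.5% type I error. The synopsis gives only the 149 deaths; it has neither the 245 nor the overall OS error rate.

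SAP 4.7.3, which specifies the OS analysis, says only that it will "compare OS between the two treatment arms by using a stratified log-rank test and the stratification factors included in the primary analysis". It gives no level. SAP 4.7.1.4 says that "all efficacy endpoints will be assessed without adjustment for multiple comparisons", on the ground that "The secondary analyses are simply intended to provide supportive evidence relating to the primary analysis".

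**PFS trigger.** The synopsis gives "Established data cut-off date: 04 October 2018" and, under statistical methods, a sample size "with total number of 255 events will provide 90% power". Protocol 5.3 has the same date with a target of 242 PFS events, and SAP 4.10 gives the reasons for it. Protocol 14.2 still has the primary analysis occur after 255 events, and 14.3.4 still bases the final PFS analysis on 255.

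**The concern.** As written, 0.8% is the level for the OS comparison as a whole. A reader who applies it at the final analysis runs a much stricter test than the one behind the 61% power in the same paragraph. A reader who recognises it as the interim level finds no final level, and might follow it with an unadjusted 5%, which slightly exceeds the OS error rate. The two sections that could settle the matter do not: SAP 4.7.3 is silent on the level, and SAP 4.7.1.4 rules out adjustment without distinguishing several endpoints from two looks at one endpoint.

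For PFS, the current protocol gives two different conditions for the primary analysis, and no section gives the power at the event count actually targeted.

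**Working it through.** **Inputs** (SAP 4.9, and protocol 14.2 where it gives the same figure): OS medians 12 and 16 months, so hazard ratio 12/16 = 0.75 under exponential survival; 149 interim and 245 final deaths; one-sided 2.5% overall; 1:1 allocation. PFS medians 4 and 6 months, so hazard ratio 0.667; 255 events. The 242 is from protocol 5.3 and SAP 4.10.

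**1. Interim OS level.** Information fraction t = 149/245 = 0.608, √t = 0.780. The two-sided O'Brien-Fleming-type spend is 4 × [1 − Φ(z₀.₉₈₇₅/√t)] = 4 × [1 − Φ(2.241/0.780)] = 0.0081, so z = 2.648. This reproduces the printed 0.8%.

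**2. Final OS level.** Solve for c so that, under the null, the chance of crossing 2.648 at the interim or c at the final look is 0.025 one-sided (bivariate normal, correlation √t). Result: c = 1.982, or 4.74% two-sided.

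**3. OS power.** The drift at 245 deaths is ln(16/12) × √245/2 = 0.2877 × 7.826 = 2.251.

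| Reading | Critical values (interim, final) | Power |
|---|---|---|
| 0.81% then 4.74% | 2.648, 1.982 | 61.0% |
| 0.8% once, at 245 deaths | –, 2.652 | Φ(2.251 − 2.652) = 34.4% |
| 0.8% at both looks | 2.652, 2.652 | 37.3% |
| 0.8% as the total OS alpha, spent over both looks | interim 0.045%, final 0.78% two-sided | 34.3% |

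Of these readings, only the first gives the stated 61%.

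**4. Effect on the decision.** The observed hazard ratio needed at 245 deaths is exp(−2z/√245): 0.776 at z = 1.982, and 0.713 at z = 2.652.

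**5. The opposite slip.** Critical values 2.652 and then an unadjusted 1.96, with the interim at 149 of 245 deaths, give a two-sided type I error of 5.24%.

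**6. Dependence on actual deaths.** The interim is timed by the PFS analysis and the final by follow-up, so neither is fixed at its planned count. Assuming 130 to 160 interim deaths (an illustrative range, with 245 at the end), the interim level runs from 0.42% to 1.11% and the final from 4.86% to 4.66%.

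**7. PFS power.** Φ(ln 1.5 × √d/2 − 1.96). At d = 255: Φ(3.237 − 1.96) = 89.9%, which reproduces the stated 90%. At d = 242: Φ(3.154 − 1.96) = 88.4%.

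**The case against.** No figure is miscalculated: 0.8% and 61% both follow from the stated design. Protocol 14.2 and SAP 4.9 print the spending function, both death counts and the overall 2.5% one-sided error together, so a statistician can derive the final level. Applying 0.8% at the end would mean ignoring the interim look and the overall error rate in the same text. The opposite slip costs only 0.24 points of type I error. SAP 4.7.1.4 calls the secondary analyses supportive, which suggests it means multiplicity across endpoints, and that is compatible with spending alpha over two OS looks. On PFS, SAP 4.10 discloses the move to 242 and explains it, and 255 events with 90% power is properly kept as the original sample-size basis.

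Most of this is right, and it limits the severity: the design is sound and its own figures agree. It does not remove the problem. The text ties 0.8% to the OS comparison itself, and a pre-specified threshold should not have to be inferred from a power figure. In the synopsis it cannot be inferred, because the 245 deaths and the overall OS error rate are absent. SAP 4.10 explains the PFS change but does not correct protocol 14.2 and 14.3.4, which are current text and conflict with protocol 5.3.

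**Conclusion.** Both parts hold, as something that should be fixed. The two-sided 0.8% is the planned interim OS level at 149 of 245 deaths. The matching final level, about 4.74% two-sided, is printed nowhere. Read literally at the final look, 0.8% takes OS power from 61.0% to 34.4% (37.3% if used at both looks) and moves the hazard ratio needed from about 0.776 to 0.713. For PFS, the protocol gives two conditions for the primary analysis, and the targeted count lowers power by about one and a half points, to 88.4%.

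These figures assume proportional hazards, 1:1 allocation, the usual normal approximation to the log-rank test and, for OS, the planned death counts. Nothing in this check shows an error in the primary PFS test itself.

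**What to change.** - **Protocol synopsis, protocol 14.2 and SAP 4.9:** label 0.8% as the planned interim OS level at 149 of 245 deaths, and add the planned final level of about 4.74% two-sided.
- **SAP 4.7.3:** state an overall two-sided 5% for OS (equivalently one-sided 2.5%, as in the power statement) with Lan-DeMets O'Brien-Fleming spending. Compute the interim level at observed deaths divided by 245, and solve the final critical value from the remaining alpha and the actual deaths. Use one convention, one-sided or two-sided, throughout the OS text.
- **SAP 4.7.1.4:** limit the statement of no adjustment to multiplicity across endpoints.
- **Protocol 14.2 and 14.3.4:** replace the 255-event trigger with the 04 October 2018 cut-off (242 PFS events targeted), and put that target beside the date in the synopsis.
- **Synopsis, protocol 14.2 and SAP 4.9:** keep 255 events and 90% power as the original design basis, and add that power at 242 events is about 88%.

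The cost is wording only, with no new patients or data. The one visible change is a slightly lower stated PFS power at the cut-off.
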